5.3 Chemoradiotherapy Trial Treatments

The treatment to be used in this trial is outlined below:

Table 3: Trial Treatment

Treatment	Dose	Dose Frequency	Route of Administration	Regimen/Treatment Period
Cisplatin	35mg/m ² (30mg/ m ² if CrCl 40-50)	Weekly, synchronous during radiotherapy	IV infusion	Weekly during radiotherapy for total 6 doses
Radiotherapy	64Gy in 32 fractions	5 daily fractions per week over 6.4 weeks.	3D- Conformal External Beam Radiotherapy	64Gy
Pembrolizumab	200 mg IV	Q3W	IV infusion	Day 1 of each 3 week cycle, until week 12 cystoscopy, for total 7 doses

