5.3.1.3.1 Administration of cisplatin

Cisplatin chemotherapy will commence on the same day as radiation therapy. After 1000ml sodium chloride 0.9% is administered as prehydration (10mmol MgSO₄ is allowed to be added as per institutional preference), cisplatin 35mg/m² in 1000mL sodium chloride 0.9% will be administered over 60 minutes. Cisplatin is commercially available. Conceivably the co-administration of dexamethasone with the chemotherapy may reduce lymphocyte counts and efficacy of pembrolizumab. Therefore, the dose of dexamethasone administered with chemotherapy will be 4mg IV rather than 8mg unless \geq G2 nausea/vomiting develops. The 5HT3 antagonist palonosetron 0.25mg IV (or equivalent 5HT3 antagonist) will be given prior to cisplatin. Other antiemetic use such as aprepitant and/or olanzapine is permissible. Dexamethasone 4 mg IV premedication given prior to cisplatin is permitted and allowed to continue at dose \leq 4mg orally daily for 2 days after administration. Increase in dexamethasone dose is permitted in discussion with the principal investigator. Urine output measurement is not necessary before cisplatin administration as high urine flow does not appear to be protective.

Cisplatin will be administered weekly during radiotherapy at 7 day intervals

The chemotherapy is to be given preferably at the beginning of each week of treatment and as far as possible on the same day of the week (or within no more than 72 hours) on each occasion throughout the course of treatment.

No more than 6 doses of cisplatin will be administered.

Patients' renal function and myeloid function will be assessed within 72 hours prior to administration of each dose of cisplatin.

The patient should be assessed by the doctor prior to proceeding with each dose of chemotherapy.

Dose modification is described in 5.3.2.1.

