5.3.1.4.3 Administration of pembrolizumab

Pembrolizumab 200mg IV, q3 weekly will be given on the same day as the cisplatin, commencing on day 1 (or within no more than 72hrs) of radiotherapy, and given every 3 weeks (weeks 1, 4, 7, 10, 13, 16 and 19).

Pembrolizumab 200 mg will be administered as a 30 minute IV infusion. Sites should make every effort to target infusion duration to be as close to 30 minutes as possible. However, given the variability of infusion pumps from site to site, a window of -5 minutes and +10 minutes is permitted (i.e., infusion duration is 30 minutes: -5 min/+10 min).

Pembrolizumab will continue after chemoradiotherapy has been completed (weeks 7, 10, 13, 16 and 19) for a total of 7 doses for the whole study, culminating with the 7th dose at week 19 of the study (12 weeks post completion of chemoradiotherapy). Pembrolizumab will continue for up to 7 doses total so long as there is

- no evidence of distant metastatic spread before this time
- no intervening administration of new anti-cancer therapy
- no evidence of locoregional progression
- no radiotherapy administered aside from that dictated in the protocol
- no pembrolizumab related AE severe toxicities as detailed in Table 6, Section 5.3.2.2 that require pembrolizumab to be withheld or discontinued.

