AEs	Grade 3	Withhold or discontinue based on the type of event. Events that require discontinuation include and not limited to: Gullain-Barre Syndrome, encephalitis		confirm etiology and/or exclude other causes		
	Grade 4 or recurrent Grade 3	Permanently discontinue				
1. Withhold or permanently discontinue pembrolizumab is at the discretion of the investigator or treating physician.						
NOTE: For participants with Grade 3 or 4 immune-related endocrinopathy where withhold of pembrolizumab is required, pembrolizumab may be resumed when AE resolves to \leq Grade 2 and is controlled with hormonal replacement therapy or achieved metabolic control (in case of T1DM).						

Dosing of cisplatin and radiation can proceed despite the development of pembrolizumab related adverse events with the exception of the dose modifications described specifically in the sections related to cisplatin and radiation.

Dosing interruptions are permitted in the case of medical / surgical events or logistical reasons not related to study therapy (e.g., elective surgery, unrelated medical events, patient vacation, and/or holidays). Participants should be placed back on study therapy within 3 weeks of the scheduled interruption, unless otherwise discussed with the Coordinating Principal Investigator. The reason for interruption should be documented in the patient's study record.

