5.3.3 Timing of Dose Administration

Pembrolizumab should be administered on Day 1 of commencement of chemoradiotherapy after all procedures/assessments have been completed as detailed on the Trial Flow Chart (Section 6.0).

Pembrolizumab 200mg IV will be given in weeks 1, 4, 7, 10, 13, 16 and 19. Treatment may be administered up to 3 days before or after the scheduled day of each cycle due to administrative reasons.

In the event of a treatment delay due to an adverse event outlined in Table 6, patients may resume pembrolizumab within 12 weeks of the due dose so long as the toxicity has resolved to Grade 1 or less and the patient is on a dose of 10mg or less of prednisolone or equivalent. Subsequent dosing of pembrolizumab will continue until week 19, but not beyond this regardless of the total number of doses that the patient has received.

All trial treatments should be administered on an outpatient basis unless discussed with the Principal Investigator/Sponsor.

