 - In hypothyroidism, thyroid hormone replacement therapy, with levothyroxine or liothyroinine, is indicated per standard of care.
 - **Grade 3-4** hyperthyroidism
 - Treat with non-selective beta-blockers (eg, propranolol) or thionamides as appropriate. Replacement of appropriate hormones may be required as the steroid dose is tapered.
- **Hepatic:**
 - For **Grade 2** events, monitor liver function tests more frequently until returned to baseline values (consider weekly).and treat with 0.5-1mg systemic prednisone or equivalent.
 - For **Grade 3-4** events, treat with intravenous 1-2mg/kg corticosteroids for 24 to 48 hours then 0.5-1mg systemic prednisone or equivalent.
 - When symptoms improve to Grade 1 or less, a steroid taper should be started and continued over no less than 4 weeks.
- **Nephritis:**
 - For **Grade 2** events, treat with corticosteroids.
 - For **Grade 3-4** events, treat with systemic corticosteroids. Permanently discontinue pembrolizumab.
 - When symptoms improve to Grade 1 or less, steroid taper should be started and continued over no less than 4 weeks.

Management of Infusion Reactions: Signs and symptoms usually develop during or shortly after drug infusion and generally resolve completely within 24 hours of completion of infusion.

Table 7 shows treatment guidelines for participants who experience an infusion reaction associated with administration of pembrolizumab.

Table 7: Infusion Reaction Treatment Guidelines

NCI CTCAE Grade	Treatment	Premedication at subsequent dosing
Grade 1 Mild reaction; infusion interruption not indicated; intervention not indicated	Increase monitoring of vital signs as medically indicated until the participant is deemed medically stable in the opinion of the investigator.	None

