Grade 2 Requires infusion interruption but responds promptly to symptomatic treatment (e.g., antihistamines, NSAIDS, narcotics, IV fluids); prophylactic medications indicated for <=24 hrs.	
Stop Infusion and monitor symptoms. Additional appropriate medical therapy may include but is not limited to:
 
 IV fluids Antihistamines NSAIDS Acetaminophen Narcotics 
Increase monitoring of vital signs as medically indicated until the participant is deemed medically stable in the opinion of the investigator.
 
If symptoms resolve within one hour of stopping drug infusion, the infusion may be restarted at 50% of the original infusion rate (e.g., from 100 mL/hr to 50 mL/hr). Otherwise dosing will be held until symptoms resolve and the participant should be premedicated for the next scheduled dose.
 
Participants who develop Grade 2 toxicity despite adequate premedication should be permanently discontinued from further trial treatment administration.
	Participant may be premedicated 1.5h (\pm 30 minutes) prior to infusion of pembrolizumab (MK-3475) with: Diphenhydramine 50 mg po (or equivalent dose of antihistamine). Acetaminophen 500-1000 mg po (or equivalent dose of antipyretic).
Grades 3 or 4 Grade 3: Prolonged (i.e., not rapidly responsive to symptomatic medication and/or brief interruption of infusion); recurrence of symptoms following initial improvement; hospitalization indicated for other clinical sequelae (e.g., renal impairment, pulmonary infiltrates) Grade 4: Life-threatening; pressor or ventilatory support indicated	
Stop Infusion. Additional appropriate medical therapy may include but is not limited to:
 
 IV fluids Antihistamines NSAIDS Acetaminophen Narcotics Oxygen Pressors Corticosteroids Epinephrine 
Increase monitoring of vital signs as medically indicated until the participant is deemed medically stable in the opinion of the investigator.
 
Hospitalization may be indicated.
 
Participant is permanently discontinued from further trial treatment administration.
	No subsequent dosing

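### Table 7 stops all 'trial treatment' after a pembrolizumab infusion reaction where pembrolizumab alone was almost certainly meant: a wording inconsistency with Section 5.3.2.2

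*Combined protocol and SAP*

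**What the plan says.** Section 5.5.1 introduces Table 7 as guidance for an "infusion reaction associated with administration of pembrolizumab". Two situations in the table lead to a permanent stop:

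- Grade 2 after premedication: "Participants who develop Grade 2 toxicity despite adequate premedication should be permanently discontinued from further trial treatment administration".
- Grade 3 or 4: "Participant is permanently discontinued from further trial treatment administration".

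A grade 1 reaction, or a first grade 2 reaction without premedication, does not trigger a stop.

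Section 5.3 is headed "Chemoradiotherapy Trial Treatments". Its Table 3, titled Trial Treatment, has three rows: cisplatin, radiotherapy and pembrolizumab. On pembrolizumab toxicity, Section 5.3.2.2 states: "Dosing of cisplatin and radiation can proceed despite the development of pembrolizumab related adverse events". It excepts only the modifications set out in the cisplatin and radiation sections.

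**The concern.** Table 7 is about one drug, but its stopping rule uses the term that Table 3 applies to all three components. Taken at its word, it tells a site to end cisplatin and radiotherapy because of a reaction to the add-on agent. Section 5.3.2.2 lets both continue.

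The inclusion criteria describe chemoradiotherapy as the definitive treatment, so what is at stake is curative-intent therapy for an individual patient. Table 7 is also the page that staff would turn to during an acute reaction, when they are least likely to cross-check another section.

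**Working it through.** **Do the two sections conflict?**

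1. The general sentence in 5.3.2.2 refers to pembrolizumab-related adverse events without limiting itself to the rows of Table 6. A reaction to a pembrolizumab infusion is such an event.
2. The exception in 5.3.2.2 does not remove the conflict. The cisplatin rules (Tables 4 and 5) turn on creatinine clearance, neutrophils and platelets. Section 5.3.4.7.2 recognises severe acute toxicity as a reason not to complete radiotherapy without a break, but does not mention infusion reactions or require a permanent stop.
3. Nothing in Table 7 limits its stop to pembrolizumab. Other entries in 5.5.1 are explicit: nephritis names pembrolizumab as the drug to stop, and pneumonitis says that cisplatin and radiation can go on if judged safe.

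The literal wording of Table 7 therefore conflicts with 5.3.2.2.

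**What would a literal stop cost?** The plan gives no figure to reproduce. The inputs are:

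- 32 fractions of 2 Gy, five per week (5.3.4.7.1)
- six weekly cisplatin doses (Table 3)
- pembrolizumab in weeks 1, 4 and 7 during radiotherapy, on the same day as cisplatin where cisplatin is due (5.3.1.4.3)

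Assume no interruptions. At a nominal infusion in week *w*, fractions already given = 5 × (*w* − 1), and cisplatin doses already given = *w* − 1, up to 6. The remainder is one smaller if that day's fraction or dose went in before the reaction.

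| Infusion | Fractions given before | Fractions lost | Gy lost | Cisplatin doses lost |
|---|---|---|---|---|
| Week 1 | 0 | 31-32 | 62-64 | 5-6 of 6 |
| Week 4 | 15 | 16-17 | 32-34 | 2-3 of 6 |
| Week 7 | 30 | 1-2 | 2-4 | 0 |
| Week 10 on | 32 | 0 | 0 | 0 |

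For week 4: 32 − 15 = 17 fractions, and 17 × 2 = 34 Gy; with that day's fraction given, 16 × 2 = 32 Gy. That is 50% to 53% of 64 Gy. The nominal counts do not depend on the weekday of the start, because 21 calendar days always contain 15 weekdays.

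Week 1 applies to grade 3-4 only, because Table 7 introduces premedication at subsequent dosing. The grade 2 trigger can first occur in week 4.

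**Sensitivity to the dosing window.** Section 5.3.3 says "Treatment may be administered up to 3 days before or after the scheduled day of each cycle due to administrative reasons". The ranges below include infusions moved by up to 3 days. A Monday start is an assumption, which fits "The chemotherapy is to be given preferably at the beginning of each week of treatment".

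- Week 1, Monday start: at most 4 fractions (8 Gy) and 1 cisplatin dose given.
- Week 4, Monday start: 14-19 fractions given, so 13-18 lost (26-36 Gy). Any weekday start: 12-19 given, so 13-20 lost (26-40 Gy).
- Week 7, Monday start: at most 3 fractions (6 Gy) left. Thursday or Friday start with the dose brought forward 3 days: 5 fractions (10 Gy) left.

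The window widens the ranges but leaves the pattern as it is: nearly everything at week 1, about half the radiation at week 4, little at week 7.

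**The case against.** The best defence is that the intent is plain. Section 5.5 is titled as supportive care for pembrolizumab. The neighbouring sentences in the grade 2 cell, on holding dosing and premedicating before the next dose, can only mean pembrolizumab, and the last column of the grade 3-4 row rules out further dosing. Section 5.5.1 itself sends the reader to 5.3.2.2 for discontinuation criteria, and the mandatory discontinuation list in 5.7 has no toxicity item. The protocol also uses the term loosely: 7.1.2.4 and 7.1.2.5 require vital signs and ECOG status before each dose of trial treatment, which cannot mean every radiotherapy fraction, and the unqualified word 'treatment' in 5.3.3 means pembrolizumab.

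All of this stands. It fixes the likely meaning and keeps the severity low. It does not correct the text: the reader still has to override a directive in Table 7 by inference from a permissive sentence elsewhere.

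A second defence is that a patient taken off trial treatment could still receive standard chemoradiotherapy. They were already planned for it, cisplatin comes through usual hospital practice, and 5.4.2 prohibits nothing in post-treatment follow-up. This does lessen the clinical harm. It is not a clean escape, however. Section 8.3 ends DMFS and LRPFS at the first non-protocol anti-cancer therapy, and Table 8 counts new anticancer therapy as progressive disease. Chemoradiotherapy continued off protocol could be recorded as a failure.

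A reader might also infer that the protocol deliberately stops chemoradiotherapy after an infusion reaction. The context just listed, and 5.3.2.2 itself, speak against that.

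**Conclusion.** Table 7 is wrong as written, at low severity. It is a wording inconsistency, not a design choice. Harm requires a site to apply Table 7 literally over 5.3.2.2. If that happened, the nominal loss of protocol treatment would be nearly all chemoradiotherapy at week 1, 32-34 of 64 Gy with 2-3 of 6 cisplatin doses at week 4, and at most 4 Gy at week 7. These figures assume no interruptions and no off-protocol continuation. The documents give no infusion-reaction rate, so how often this could arise is unknown.

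It is tempting to add that the wording inflates the unacceptable-toxicity rate. The documents do not support that. A grade 3-4 infusion reaction already counts as an unacceptable toxicity. Only a grade 2 reaction despite premedication at week 4 could add an event, through lost cisplatin doses. That would depend on which cisplatin criterion applies (two or more doses withheld in 3.1 and 8.1; more than two omitted in 4.2.4.1) and on a rate that is not given. No effect on the endpoint is claimed.

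**What to change.** In both Table 7 rows, replace *further trial treatment administration* with *further pembrolizumab administration*. Then add: *Cisplatin and radiotherapy may continue per Section 5.3.2.2 once the reaction has resolved and if judged safe by the investigator.*

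The added sentence follows the existing pneumonitis entry and keeps clinical judgement after a severe reaction. The cost is a few words in two rows and one sentence at the next amendment. No visit, procedure or analysis changes.

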5.6 Diet/Activity/Other Considerations

5.6.1 Diet

Participants should maintain a normal diet unless modifications are required to manage an AE such as diarrhea, nausea or vomiting.

5.6.2 Contraception

Pembrolizumab may have adverse effects on a fetus in utero. Furthermore, it is not known if pembrolizumab has transient adverse effects on the composition of sperm. Non-pregnant, non-

breast-feeding women may be enrolled if they are willing to use 2 methods of birth control or are considered highly unlikely to conceive. Highly unlikely to conceive is defined as 1) surgically sterilized, or 2) postmenopausal (a woman who is ≥ 45 years of age and has not had menses for greater than 1 year will be considered postmenopausal), or 3) not heterosexually active for the duration of the study. The two birth control methods can be either two barrier methods or a barrier method plus a hormonal method to prevent pregnancy. Participants should start using birth control from study Visit 1 throughout the study period and continue until 120 days after the last dose of study therapy.

The following are considered adequate barrier methods of contraception: diaphragm, condom (by the partner), copper intrauterine device, sponge, or spermicide. Appropriate hormonal contraceptives will include any registered and marketed contraceptive agent that contains an estrogen and/or a progestational agent (including oral, subcutaneous, intrauterine, or intramuscular agents).

Participants should be informed that taking the study medication may involve unknown risks to the fetus (unborn baby) if pregnancy were to occur during the study. In order to participate in the study, they must adhere to the contraception requirement (described above) for the duration of the study and during the follow-up period defined in section 7.2.2-Reporting of Pregnancy and Lactation to the Sponsor and to Merck. If there is any question that a participant will not reliably comply with the requirements for contraception, that participant should not be entered into the study.

5.6.3 Use in Pregnancy

If a participant inadvertently becomes pregnant while on treatment with pembrolizumab, the participant will immediately be removed from the study. It is the responsibility of the site investigators or their designees to report all pregnancy exposures within 24 hours of becoming aware to the BaCT Trial Centre and to Merck Global Safety using the trial specific Pregnancy Reporting Form. The site will continue to contact the participant at least monthly and document the participant's status until the pregnancy has been completed or terminated. The outcome of the pregnancy will be reported to the Sponsor and to Merck without delay and within 24 hours to the Sponsor and to Merck if the outcome is a serious adverse experience (e.g., death, abortion, congenital anomaly, or other disabling or life-threatening complication to the mother or newborn).

The study investigator will make every effort to obtain permission to follow the outcome of the pregnancy and report the condition of the fetus or newborn to the Sponsor. If a male participant impregnates his female partner the study personnel at the site must be informed immediately and the pregnancy reported to the Sponsor and to Merck and followed as described above and in Section 7.2.4.

5.6.4 Use in Lactating Women

It is unknown whether pembrolizumab is excreted in human milk. Since many drugs are excreted in human milk, and because of the potential for serious adverse reactions in the lactating infant, participants who are breast-feeding are not eligible for enrolment.

5.7 Participant Withdrawal/Discontinuation Criteria

Participants may withdraw consent at any time for any reason or be dropped from the trial at the discretion of the investigator should any untoward effect occur. A patient who withdraws consent prior to commencement of pembrolizumab and chemoradiotherapy may be replaced to ensure 30 patients in total are treated with the combination. In addition, a participant may be withdrawn by the investigator or the Sponsor if enrolment into the trial is inappropriate, the trial plan is violated, or for administrative and/or other safety reasons. Specific details regarding discontinuation or withdrawal are provided in Section 7.1.4– Other Procedures.

A participant must be discontinued from trial treatment for any of the following reasons:

- Confirmed radiographic locoregional or metastatic disease progression
- Initiation of new anti-cancer therapies
- Intercurrent illness that prevents further administration of treatment
- Investigator's decision to withdraw the participant
- The participant has a confirmed positive serum pregnancy test
- Noncompliance with trial treatment or procedure requirements
- The participant is lost to follow-up
- Administrative reasons
- The participant or legal representative (such as a parent or legal guardian) withdraws consent.
- Patient decision to withdraw

The End of Treatment and Follow-up visit procedures are listed in Section 6 (Protocol Flow Chart) and Section 5.2.6 (Evaluations during follow-up)

After the end of treatment visit, each participant will be followed as per the follow-up schedule outlined in Section 5.2.6. Participants will be followed until end of study or until withdrawal of consent, for disease status, initiation of new anticancer therapies, and overall survival.

6.0 TRIAL FLOW CHART

6.1 Study Flow Chart

	Screening	Chemoradiotherapy						Pembrolizumab Treatment Period					End of Treatment (j)	Post Treatment Review	Follow Up (l)
		Week						Week							
	-42 to -1 days	1	2	3	4	5	6	7	10	13	16	19	23	31	
Informed consent	X														
Clinic Assessment (a)	X	X	X	X	X	X	X	X	X	X	X	X	X	X	X
Lab Tests (b)															
FBE	X	X	X	X	X	X	X	X	X	X	X	X	X	X	
UECr	X	X	X	X	X	X	X	X	X	X	X	X	X	X	
LFTs	X	X	X	X	X	X	X	X	X	X	X	X	X	X	
TSH, T3, T4	X	X													
Coagulation	X														
Cisplatin		X	X	X	X	X	X								
Radiotherapy		X	X	X	X	X	X	X (i)							
Pembrolizumab (c)		X			X			X (i)	X	X	X	X			
Imaging CT Ch/Abdo/Pelvis (d)	X												X	X	X
Cystoscopy(e)	X												X	X	X
Urine Cytology		X											X	X	X
Biomarker blood (f)		X						X					X		
Urine for biomarker		X						X					X		
Pregnancy Test (g)	X	X													
Con Meds	X	X	X	X	X	X	X	X	X	X	X	X			
Adverse Events (h)	X	X	X	X	X	X	X	X	X	X	X	X	X		
Post-study anticancer therapy Status													X	X	X
Documentation of Disease Status													X	X	X
Survival Status													X	X	X

- a. Clinical Assessment: Pre-Treatment - Prior medical and therapeutic history (including concomitant medications, histological documentation of malignancy, full physical exam, ECOG performance status, vital signs and prior anticancer therapy. During Treatment and End of Treatment Visits- adverse events, vital signs, concomitant medications, ECOG performance status and directed physical examination. ECOG performance status assessment during screening must take place within 10 days of treatment. During Follow-Up: Vital signs, ECOG performance status and directed physical exam.
- b. Laboratory tests need to be performed within 3 days of each treatment related visit, except for the first visit, when these can be performed within 10 days.
- c. Pembrolizumab given if no contraindications based on AE assessment
- d. CT chest/abdomen/pelvis. *Note:* Both oral and IV contrast is required. In the event of known allergy to contrast, an MRI abdomen/pelvis may be performed as an alternative. Method of tumour assessment should be consistent throughout all visits Additional scans as clinically indicated.
- e. Any additional cystoscopic assessment is at the clinician discretion during this period.
- f. Blood – 50ml of blood drawn at each of 3 visits: as per the PCR-MIB Biomarker Laboratory Manual
- g. Patients should have a negative urine or serum pregnancy test within 72 hours prior to receiving the first dose of study medication.
- h. Adverse Events: To be graded according to the NCI Common Terminology Criteria for Adverse Events Version 4.03
- i. Week 7 Pembrolizumab dose will occur in same week as last 2 days of radiotherapy
- j. End of treatment review occur either at Week 23, or 28 days after last treatment for patients who discontinue for either progression before week 19, or other reason i.e. toxicity
- k. CT chest/abdomen/pelvis, cystoscopy and urine cytology only need to be performed at End of Treatment visit if these have not been performed at Week 19, for instance if patients has come of study for toxicity prior to Week 19.
- l. Follow Up visits will be 3 monthly for 12 months after the End of Treatment visit, then 6 monthly for 18 months, then 12 monthly thereafter under study closure, with cystoscopic assessment, urine cytology collection and CT C/A/P within 28 days of each follow up visit. Patients with either local or distant progression do not require vital sign, directed physical examination, urine cytology, or cystoscopy assessment at each visit. Patients with local progression should continue to receive radiological evaluation for assessment of distant metastatic disease. Patients with distant progression should receive radiological evaluation at the discretion of the investigator

